5.4 Screen failures

Screen failures are defined as study participants who consent to participate in the clinical study but are not subsequently entered in the study. A minimal set of screen failure information is required to ensure transparent reporting of screen failure study participants to meet the Consolidated Standards of Reporting Trials (CONSORT) publishing requirements and to respond to queries from regulatory authorities. Minimal information includes demography, screen failure details, eligibility criteria, and any SAE.

5.4.1 Rescreening

Individuals who do not meet the criteria for participation in this study (screen failures) may be rescreened. Study participants may be rescreened under conditions such as the following:

- Study participant ingests grapefruit (as beverage, fruit, or supplements) within 72 hours before first administration of study medication.
- If a study participant does not meet the exclusion criteria at Screening or on Day -1 due to an out-of-range laboratory result or a minor illness, she can be rescreened once at the discretion of the Investigator. Provided all inclusion criteria are met at the second screening, the study participant can be included.

Study participants may be included if the repeat values for the laboratory screening criteria are within normal ranges and/or if repeat values show normalization of the out-of-range safety laboratory values, and/or after the study participant makes a complete recovery from the mild or moderate illness, and if all other screening criteria are met.

Tests that result in ALT, AST, or ALP up to 25% above the exclusion limit may be repeated once for confirmation; if the results are out of range again, the study participant cannot be included.

Rescreened study participants will be assigned a new participant number.

6 STUDY TREATMENTS

Study treatment is defined as any investigational treatment(s), marketed product(s), placebo, or medical device(s) intended to be administered to a study participant according to the study protocol.

6.1 Treatments administered

A summary of the study treatments administered is provided in [Table 6-1](#). Treatments will be administered in an open-label fashion and study participants will be dosed in an upright position. On PK sampling days, study participants must remain semi-recumbent until 4 hours after the morning dose of PSL (apart from when required to do otherwise for study assessments such as vital signs, ECGs, etc).

Table 6-1: Study medications administered

Study Medication Name:	Padsevonil
Dosage formulation:	Tablets
Unit dose strength(s)/Dosage level(s):	100mg tablets for BID dosing
Route of Administration:	Oral
Dosing instructions:	
All treatments will be administered orally with 8oz (240mL) water. The use of beverages between 1h predose and 2h postdose should be limited to a maximum of 100mL (in order to keep groups comparable with respect to period of dosing). Study participants will complete a light meal 30 minutes prior to each morning dose of PSL and will complete a standard meal 30 minutes prior to the evening dose of PSL.
 
Treatments will be administered in an open-label fashion. Study participants will be dosed in an upright position. On PK sampling days, study participants must remain semi-recumbent until 4 hours after the morning dose of PSL (apart from when required to do otherwise for study assessments such as vital signs, ECGs, etc).

Packaging and Labeling	Padsevonil tablets are manufactured, packaged, and labeled according to Good Manufacturing Practice guidelines and applicable laws and regulations.
Manufacturer	UCB

Study Medication Name:	Single dose Microgynon 30® (ethinyl estradiol 30µg+levonorgestrel 150µg)
Dosage formulation:	Tablets
Unit dose strength(s):	(ethinyl estradiol 30µg+levonorgestrel 150µg)
Route of Administration:	Oral
Dosing instructions:	Dosing instructions are provided in the UP0035 IMP Handling Manual (IMP Instructions for Handling).
Packaging and Labeling	Tablets are manufactured, packaged, and labeled according to Good Manufacturing Practice guidelines and applicable laws and regulations
Manufacturer	Bayer

IMP=investigational medicinal product; PSL=padsevonil

6.2 Preparation, handling, storage, and accountability requirements

The Investigator or designee must confirm appropriate temperature conditions have been maintained during transit for all study medications received and any discrepancies are reported and resolved before use of the study medication.

Only participants enrolled in the study may receive study medication and only authorized site staff may supply or administer study medication. All study medication must be stored in a secure, environmentally controlled, and monitored (manual or automated) area in accordance with the labeled storage conditions with access limited to the Investigator and authorized site staff.

The Investigator, institution, or the head of the medical institution (where applicable) is responsible for study medication accountability, reconciliation, and record maintenance (ie, receipt, reconciliation, and final disposition records).

In case an out-of-range temperature is noted, it must be immediately reported as per instructions contained in the UP0035 IMP Handling Manual.

Further guidance and information for the final disposition of unused study medication are provided in the UP0035 IMP Handling Manual.

6.2.1 Drug accountability

A Drug Accountability form will be used to record study medication dispensing and return information on a by-study participant basis and will serve as source documentation during the course of the study. Details of any study medication lost, damaged (due to breakage or wastage), not used, partially used, disposed of at the study site, or returned to the Sponsor or designee must also be recorded on the appropriate forms. All supplies and pharmacy documentation must be made available throughout the study for UCB (or designee) to review.

The Investigator (or designee) is responsible for retaining all used, unused, and partially used containers of study medication until returned or destroyed.

The Investigator may assign some of the Investigator's duties for drug accountability at the study site to an appropriate pharmacist/designee.

The Investigator must ensure that the study medication is used only in accordance with the protocol.

Periodically, and/or after completion of the clinical phase of the study, all used (including empty containers)/partially used, unused, damaged, and/or expired study medication must be reconciled and either destroyed at the site according to local laws, regulations, and UCB standard operating procedures or returned to UCB (or designee). Investigational medicinal product intended for the study cannot be used for any other purpose than that described in this protocol.

6.3 Measures to minimize bias: randomization and blinding

This study is an open-label study; therefore, no study personnel or study participants will be blinded.

A contract research organization (CRO; ie, ICON) randomization biostatistician will create the program to generate the randomization code. A dummy randomization schedule will be prepared by the randomization biostatistician (a cross-over 2x2 scheme with 2 treatment sequences) and reviewed by the Clinical Study Biostatistician in order to ensure that the code meets the study requirements.

After finalization of the dummy code, the randomization program will be run with a different seed number to create the final randomization list; the final list will be generated and will be

reviewed by a quality control randomization biostatistician. The treatment assignment will be random.

Copies of the randomization lists will be sent before the start of the study in a secure fashion directly from the contracted CRO to:

- Sponsor Patient Safety staff for SAE reporting
- Bioanalytical staff (to identify samples to be measured)
- A member of pharmacy involved in IMP preparation and dispensing
- The Clinical Study Biostatistician/Statistical Programmer

In addition, staff involved in the analysis of PK data, such as a representative from the UCB Clinical Pharmacology/Modeling and Simulation team and a monitor, will have access to the data during the study.

Once the Investigator determines that the study participant is eligible for the study, and before IMP administration, a central person in charge of issuing the randomization numbers will manually allocate a randomization number to the study participant and communicate the randomization assignment to the Site Pharmacist. Each specific randomization number will be linked to the treatment allocation on the randomization schedule, which will be dispensed by the site pharmacist. The randomization numbers will also be recorded in the eCRF.

Each study participant will receive a 5-digit study participant number, from a range of numbers supplied by UCB Clinical Data Operations, Technology, and Standards, assigned at Screening that will serve as the study participant identifier throughout the study. The study participant number will be required in all communication between the Investigator/designee.

6.3.1 Procedures for maintaining and breaking the treatment blind

6.3.1.1 Maintenance of study medication blind

This is not applicable as this is an open-label study.

6.3.1.2 Breaking the study medication blind in an emergency situation

This is not applicable as this is an open-label study.

6.4 Treatment compliance

Study participant compliance will be ensured by the administration of study medication by designated site personnel. Drug accountability must be recorded on the Drug Accountability form.

6.5 Concomitant medication(s)/treatment(s)

6.5.1 Permitted concomitant treatments (medications and therapies)

The use of concomitant medications during this study should be avoided unless necessary to treat AEs or unless approved on a case-by-case basis prior to enrollment. The use of any concomitant

medications should be approved by the Sponsor in advance, in writing, when possible. The following concomitant medications are permitted during the study:

- Paracetamol for the treatment of mild symptoms (eg, headache or other pain), given at most every 6 hours to 8 hours, not exceeding 2g/day, and with a total of no more than 5g over 7 days
- Ibuprofen
- Inhaled corticosteroids for seasonal rhinitis

6.5.2 Prohibited concomitant treatments (medications and therapies)

With the exception of permitted concomitant treatments listed in Section 6.5.1, prescription or nonprescription medicines, including OTC remedies and herbal and dietary supplements (including St John's Wort), are prohibited within 14 days or 5 half-lives (whichever is longer) before administration of PSL and during the Treatment Period, unless required to treat an AE. Drugs of unknown half-life are prohibited within 14 days before administration of PSL and during the Treatment Period, unless required to treat an AE. The use of any inducers or inhibitors of CYP2C19 or CYP3A4 is prohibited.

Combined (estrogen and progestogen containing) hormonal contraception and progesterone only hormonal contraceptive methods are not permitted in this study (Section 10.4).

6.5.3 Rescue medication

Not applicable.

6.6 Dose modification

No PSL dose modifications are permitted during the study for an individual study participant.

6.7 Treatment after the end of the study

There are no plans for continued study participant care or treatment after the end of the study.

7 DISCONTINUATION OF STUDY MEDICATION AND STUDY PARTICIPANT DISCONTINUATION/WITHDRAWAL

7.1 Discontinuation of study medication

Study medication will be stopped if the study participant develops a medical condition, laboratory abnormality, ECG change, or other finding that, in the opinion of the Investigator, compromises the study participant's ability to participate or safety.

[figure not shown]
In all cases the study participant should be followed until the condition has resolved as agreed by the Investigator and the UCB Study Physician. Study participants withdrawn from the study should complete PSL tapering. Investigators should contact the UCB Study Physician, in advance whenever possible, to discuss the withdrawal of a study participant and the appropriate schedule of tapering under the circumstances. No restart will be allowed.

7.1.1 Liver chemistry stopping criteria

Discontinuation of study medication for abnormal liver function should be considered by the Investigator when a study participant meets 1 of the conditions outlined in Figure 7-1 or if the Investigator believes that it is in best interest of the study participant.

Study medication will be discontinued immediately and permanently for a study participant if liver chemistry stopping criteria are met.

Figure 7-1: Liver chemistry stopping algorithm

ALT=alanine aminotransferase; AST=aspartate aminotransferase; INR=international normalized ratio; SAE=serious adverse event; ULN=upper limit of normal

Liver safety–suggested actions and follow-up assessments for potential drug-induced liver injury (PDILI) are provided in Appendix 6 (Section 10.6).

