Study participants enrolled in the Treatment Sequence A group will start with up-titration of PSL with increasing repeated BID doses to reach a steady-state dose level of PSL 400mg BID. Once at steady-state, on the morning of Day 13, study participants will receive a single dose of OC in addition to PSL 400mg BID. From Day 15 to Day 19, PSL will be tapered from a dose of 400mg BID to 100mg BID. On Day 20, study participants will start the 14-day Washout Period. On Day 34, a single dose of OC will be administered followed by 2 days of PK measurements. An SFU Visit will occur between Day 41 to Day 44.

Sequence B

Study participants enrolled in the Treatment Sequence B group will start with the single dose of OC on the morning of Day 1 followed by 2 days of PK measurements and will then start the 14-day Washout Period. At the end of the Washout Period, the Treatment Sequence B group will start with up-titration of PSL treatment with increasing repeated BID doses to reach a steady-state dose level of PSL 400mg BID. Once at steady-state, on the morning of Day 30, study participants will receive a single dose of OC in addition to PSL 400mg BID. From Day 32 to Day 36, PSL will be tapered from a dose of 400mg BID to 100mg BID. All study participants will complete an SFU Visit between Day 43 and Day 46.

Part 2

Protocol Amendment 2 introduces Part 2 (Schematic shown in [Table 1-3](#)) in which 26 study participants are planned to be enrolled, due to the stop of Part 1 after the completion of 14 study participants.

Sequence A

All study participants enrolled in Part 2, Treatment Sequence A, will be administered PSL 100mg BID on Day 1, with titration to 200mg BID for Day 2 to Day 10. A single dose of OC is administered on the morning of Day 9, at which time PSL is at steady state. Pharmacokinetic assessments will be collected according to the Schedule of Activities. To taper, 100mg BID of PSL will be given on Day 11. Starting on Day 12, the study participants will then complete a Washout Period for 14 days followed by a return to the clinic on Day 25 for the OC-only dosing on Day 26. Pharmacokinetic samples will be collected on Days 26, 27, and 28. An SFU Visit will occur between Day 33 and Day 40.

Sequence B

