1.3.1.1 Part 1 Sequence A

Table 1-4: Schedule of activities- Part 1 Treatment Sequence A

	Screening	Baseline	OC+PSL								Washout (14 Days)	OC			EOS/ SFU/ EDV ^a	
			1	2 to 3	4 to 5	6 to 12	13	14	15 to 16	17 to 18		19	34	35		36
Day	-29 to -2	-1	1	2 to 3	4 to 5	6 to 12	13	14	15 to 16	17 to 18	19	20 to 33	34	35	36	41 to 44
Written informed consent	X															
Demographics and baseline characteristics	X															
Inclusion /Exclusion criteria verification	X	X	X													
General medical /medications/ procedures history	X	X										X (D33)				
Suicidality Risk Assessment (C-SSRS) ^b	X	X										X (D33)				X
Psychiatric and mental status evaluation	X	X	X	X	X	X	X	X	X	X	X					X
Physical examination ^c	X	X	X	X	X	X	X	X	X	X	X	X (D33)				X
Vital signs ^d	X	X	X	X	X	X	X	X	X	X	X		X	X	X	X
Pregnancy test	X	X										X (D33)				
Hematology, clinical chemistry, urinalysis	X	X									X	X (D33)				X
Serology (HIV, HBsAg, HEV, syphilis, and HCV-Ab)	X															

Table 1-4: Schedule of activities- Part 1 Treatment Sequence A

Day	Screening	Baseline	OC+PSL								Washout (#4 Days)	OC			EOS/ SFU/ EDV ^a		
			1	2 to 3	4 to 5	6 to 12	13	14	15 to 16	17 to 18		19	20 to 33	34		35	36
12-lead ECG	X	X	X	X ^c	X ^c	X ^c	X	X	X	X	X						X
Urine and cotinine drug screen, and alcohol breath test	X	X															
Recording of adverse events/medical procedures	X	X	X	X	X	X	X	X	X	X	X	X (D33)	X (D33)	X	X	X	X
Blood sampling for genotyping of drug metabolizing enzymes and/or transporters		X															
Admit to clinic		X															
Administer PSL			X	X	X	X	X	X	X	X	X						
Administer OC								X						X			
Blood sampling for PSL PK levels					X ^f	X ^f	X ^f	X ^f	X ^f	X ^f	X ^f						
Blood sampling for OC PK levels								X ^g	X ^g	X ^g	X ^g			X ^g	X ^g	X ^g	
Blood sampling for cross-validation ^h						X											
Discharge														X (D20 or D21) ^j			X

C-SSRS=Columbia Suicide Severity Rating Scale; EOS=End of Study; EDV=Early Discontinuation Visit; ECG=electrocardiogram; h=hour(s); HbsAg-Ab=HepB surface antigen antibodies; HCV-Ab=HepC virus antibodies; HEV=hepatitis E virus; HIV=human immunodeficiency virus; OC=oral contraceptive; PK=pharmacokinetic; PSL=padsevonil; SFU=Safety Follow-Up

- ^a If a study participant discontinues early, SFU procedures should be completed as the EDV. Upon early termination/withdrawal, the study participant will be encouraged to complete SFU assessments following the last dose of study medication.

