- ^b All study participants will complete the "Screening/Baseline" version of the C-SSRS during Screening (assessing the past 6 months), followed by the "Since Last Visit" version at subsequent visits.
- ^c At Screening, Baseline (Day -1), Day 6, and Day 12, a full physical examination will be performed. On all other days a physical examination is performed, it will be a brief physical examination (Section 8.3.1). On Days 7 to 11, physical examination will not be performed.
- ^d Oral or aural body temperature (temperature must be performed using the same method in any individual study participant on all occasions), pulse rate, respiratory rate, and blood pressure will be assessed. Vital signs (to be taken before blood collection for laboratory tests) will consist of 1 pulse and 1 blood pressure measurement.
- ^e ECG will be completed on Days 2, 4, 6, and 12 only of multiple day periods during Treatment Sequence A.
- ^f During the OC+PSL Treatment Period, trough levels of PSL will be collected on morning before PSL dosing on Day 2, Day 4, Day 6, Day 8 and Day 10. Additional blood sampling for PK analysis will be taken on Day 12 (PSL PK) before (predose) and after PSL morning dose at 0.25h, 0.5h, 1h, 1.5h, 2h, 3h, 4h, 6h, 8h, 12h postdose and on Day 13 (PSL and OC PK) before (predose) and after the PSL and OC morning dose at 0.25h, 0.5h, 1h, 1.5h, 2h, 3h, 4h, 6h, 8h, 12h, 24h (before morning PSL dose on Day 14), and 48h (before morning PSL dose on Day 15) postdose.
- ^g During OC+PSL Treatment Period, blood sampling for OC PK analysis will be taken on Day 13 (before OC+PSL morning dose) and after PSL and OC morning dose at 0.25h, 0.5h, 1h, 1.5h, 2h, 3h, 4h, 6h, 8h, 12h, 24h (Day 14), 36h (Day 14), and 48h (Day 15) postdose. During the single-dose OC period, PK blood samples will be taken on Day 34 at predose and 0.25h, 0.5h, 1h, 1.5h, 2h, 3h, 4h, 6h, 8h, 12h, 24h (Day 35), 36h (Day 35), and 48h (Day 36) postdose.
- ^h Mitra™ (finger prick) blood samples will be taken at 0.5h, 1h, 3h, 6h, 12h postdose on Day 12 only for selected study participants. See Section 8.1.1 for details about selection.
- ⁱ The study participant can be discharged on Day 20 or Day 21, at the discretion of the principal investigator.

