- b All study participants will complete the "Screening/Baseline" version of the C-SSRS during Screening (assessing the past 6 months), followed by the "Since Last Visit" version at subsequent visits.
- c At Screening, Baseline (Day -1), Day 23, and Day 29, a full physical examination will be performed. On all other days a physical examination is performed, it will be a brief physical examination (Section 8.3.1). On days 24-28, physical examination will not be performed.
- d Oral or aural body temperature must be performed using the same method in any individual study participant on all occasions.), pulse rate, respiratory rate, and blood pressure will be assessed. Vital signs (to be taken before blood collection for laboratory tests) will consist of 1 pulse and 1 blood pressure measurement.
- e ECG will be completed on Days 19, 21, 23, and 29 only of multiple day periods during Treatment Sequence B.
- f During the OC+PSL Treatment Period, trough levels of PSL will be collected on morning before PSL dosing on Day 19, Day 21, Day 23, Day 25, and Day 27. Additional blood sampling for PK analysis will be taken on Day 29 (PSL PK) before (predose) and after PSL morning dose at 0.25h, 0.5h, 1h, 1.5h, 2h, 3h, 4h, 6h, 8h, 12h postdose and on Day 30 (PSL PK) before (predose) and after the PSL and OC morning dose at 0.25h, 0.5h, 1h, 1.5h, 2h, 3h, 4h, 6h, 8h, 12h postdose. In addition, blood samples will be obtained prior to the morning dose on Day 31 and prior to the morning dose on Day 32.
- g During the single-dose OC period, PK blood samples will be taken on Day 1 at predose and 0.25h, 0.5h, 1h, 1.5h, 2h, 3h, 4h, 6h, 8h, 12h, 24h (Day2), 36h (Day 2), and 48h (Day 3) postdose. During OC+PSL Treatment Period, blood sampling for OC PK analysis will be taken on Day 30 (before OC+PSL morning dose) and after PSL and OC morning dose at 0.25h, 0.5h, 1h, 1.5h, 2h, 3h, 4h, 6h, 8h, 12h, 24h (Day 31), 36h (Day 31), and 48h (Day 32) postdose.
- h Mitra™ (finger prick) blood samples will be taken at 0.5h, 1h, 3h, 6h, 12h postdose on Day 29 only. See Section 8.1.1 for details about selection.
- i The study participant can be discharged on Day 37 or Day 38, at the discretion of the principal investigator.

1.3.2 Part 2

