10.6 Appendix 6: Liver safety—suggested actions and follow-up assessments

Participants with PDILI must be assessed to determine if study medication must be discontinued. In addition, all concomitant medications and herbal supplements that are not medically necessary should be discontinued.

Investigators should attempt to obtain information on study participants in the case of study medication discontinuation to complete a final evaluation.

Study participants with PDILI should not be withdrawn from the study until investigation and monitoring are complete. All results of these evaluations and observations, as well as the reason(s) for study medication discontinuation and/or participant withdrawal (if applicable), must be recorded in the source documents. The eCRF must document the primary reason for discontinuation of study medication.

A specific monitoring plan must be agreed between the UCB Study Physician and the Investigator for study participants who have ALT >5 ULN. The monitoring plan should include any necessary follow-up assessments (until resolution of the abnormal lab values).

Phase 1 liver chemistry stopping criteria are designed to assure participant safety and to evaluate liver event etiology ([Table 10-2](#)).

Table 10-2: Phase I liver chemistry stopping criteria and follow-up assessments

Liver Chemistry Stopping Criteria – Liver Stopping Event	
ALT-absolute	
ALT \geq 3xULN
 
If ALT \geq 3xULN AND bilirubin \geq 2xULN (>35% direct bilirubin) OR international normalized ratio (INR) > 1.5, report as a serious adverse event (SAE).^{a,b}
 
See additional actions and follow-up assessments listed below.

Suggested Actions and Follow-up Assessments	
Actions	Follow-Up Assessments

This document cannot be used to support any marketing authorization application and any extensions or variations thereof.

REDACTED COPY

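### While PSL is being dosed, the only scheduled safety laboratory sample is on the last dosing day, so on scheduled results the mandatory liver stop can spare at most 200 mg of PSL

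*Protocol*

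**What the plan says.** Protocol Section 7.1.1 gives the rule: "Study medication will be discontinued immediately and permanently for a study participant if liver chemistry stopping criteria are met". Table 10-2 in Section 10.6 sets the trigger at ALT of at least 3xULN, and that section gives the purpose: "Phase 1 liver chemistry stopping criteria are designed to assure participant safety and to evaluate liver event etiology". Figure 7-1 is not shown in the text available, so the threshold here rests on Table 10-2.

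Section 8.3.4 leaves the timing of laboratory tests to the Schedules of Activities. The row headed "Hematology, clinical chemistry, urinalysis" marks these days:

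| Schedule | Before PSL | On a PSL dosing day | After PSL |
|---|---|---|---|
| Part 1, Sequence A (Table 1-4) | Screening, Day -1 | Day 19 | Day 33, SFU |
| Part 1, Sequence B (Table 1-5) | Screening, Day -1, Day 17 | Day 36 | SFU |
| Part 2, Sequence A (Table 1-6) | Screening, Day -1 | Day 11 | Day 25, SFU |
| Part 2, Sequence B (Table 1-7) | Screening, Day -1, Day 17 | Day 28 | SFU |

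The Table 1-5 row is damaged in the extracted protocol. Day 36 is read from SAP Table 2-5 and agrees with the protocol's summary of changes.

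Each on-PSL sample falls on the final day of dosing. For Part 1, Sequence A, Section 1.1.5 says: "From Day 15 to Day 19, PSL will be tapered from a dose of 400mg BID to 100mg BID". The other three schedules also end at 100mg BID. Section 7.1 adds: "Study participants withdrawn from the study should complete PSL tapering".

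**The concern.** A stopping rule can act only on data it receives. The QTc stop in Section 7.1.2 is well supplied: in Part 1, Sequence A, ECGs are scheduled on Days 6, 12, 13 and 14, all at 400mg BID. The liver stop gets its first scheduled on-drug result when dosing is about to end.

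An earlier stop depends on someone deciding to test, and a rise in ALT without symptoms gives no prompt. The same sample also feeds the potential Hy's Law definition in Section 8.4.6 and the eosinophil, neutrophil and platelet thresholds in withdrawal criterion 12 of Section 7.3. What is at stake is continued PSL dosing in a healthy volunteer who already meets a mandatory stopping criterion.

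**Working it through.** **Inputs.** Daily PSL doses come from Tables 1-2 and 1-3, and laboratory days from the rows above. Daily amount = 2 x the BID dose. Sequence B has the same PSL doses as Sequence A, 17 days later.

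**The plan's own durations reproduce.**
- Part 1: 1 + 2 + 2 + 9 + 2 + 2 + 1 = 19 days.
- Part 2: 1 + 9 + 1 = 11 days.

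**Total PSL.**
- Part 1: 200 + 2x400 + 2x600 + 9x800 + 2x600 + 2x400 + 200 = 11,600 mg.
- Part 2: 200 + 9x400 + 200 = 4,000 mg.

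**PSL that the present schedule can spare.** This is the total minus what is given before the sampling day.
- Part 1: 11,600 - 11,400 = 200 mg; 200/11,600 = 1.7%.
- Part 2: 4,000 - 3,800 = 200 mg; 200/4,000 = 5%.

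The 200 mg needs a pre-dose sample and a result before that morning's dose. A result between the two doses spares 100 mg, and a later one spares nothing. The schedules do not say whether the sample is taken before or after dosing.

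**Samples at top dose.** Part 1: 0 of 9 days at 400mg BID (Days 6-14 or 23-31). Part 2: 0 of 9 days at 200mg BID (Days 2-10 or 19-27).

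**PSL that could be stopped with a tube at an existing draw.** In Part 1, Sequence A, "trough levels of PSL will be collected on morning before PSL dosing on Day 2, Day 4, Day 6, Day 8 and Day 10", and also "Additional blood sampling for PK analysis will be taken on Day 12 (PSL PK) before (predose) and after PSL morning dose". In Sequence B, "Additional blood sampling for PK analysis will be taken on Day 29 (PSL PK) before (predose) and after PSL morning dose". In Part 2 the matching pre-dose draw is on Day 8 or Day 25. Turnaround is not stated, so the lower figure assumes a result before the next morning's dose and the upper figure a result before the same evening's dose. The Part 1 taper is 2x600 + 2x400 + 200 = 2,200 mg; the Part 2 taper is 200 mg.

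| Pre-dose draw | Full days already at top dose | Given before | Still stoppable | Still stoppable if the full taper is given |
|---|---|---|---|---|
| Part 1, Day 8/25 | 2 | 3,800 mg | 7,000 to 7,400 mg (60% to 64%) | 4,800 to 5,200 mg |
| Part 1, Day 10/27 | 4 | 5,400 mg | 5,400 to 5,800 mg (47% to 50%) | 3,200 to 3,600 mg |
| Part 1, Day 12/29 | 6 | 7,000 mg | 3,800 to 4,200 mg (33% to 36%) | 1,600 to 2,000 mg |
| Part 2, Day 8/25 | 6 | 2,600 mg | 1,000 to 1,200 mg (25% to 30%) | 800 to 1,000 mg |

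Example, Part 1 Day 12: 11,600 - 7,000 - 800 = 3,800 mg, or 11,600 - 7,000 - 400 = 4,200 mg; subtracting 2,200 gives 1,600 and 2,000 mg.

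**The case against.** The strongest reply is that the plan is adequate for the risk. Section 2.3 describes mainly CNS effects, exclusion criteria 17 to 19 are strict on liver tests and liver disease, and dosing lasts 19 or 11 days. Laboratory change is only an Other endpoint. The Investigator may test at any time (Section 10.2), unscheduled safety samples are allowed (Section 8), and time points can be added without an amendment (Section 8.1). Full physical examinations, which cover the hepatic system, are scheduled at top dose. Milligrams spared are doses, not risks, and no ALT event rate or time course is given. Fourteen participants have completed Part 1, and SAP Section 1 says nobody will enter Part 2.

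Most of this stands, and it sets the size of the point. It does not supply the missing input: discretionary testing needs a prompt, and a physical examination does not measure ALT. Stopping the study limits the practical effect without making the schedule sound.

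Stronger readings are tempting but unsupported:
- **No safety laboratory data once PSL has begun.** Wrong. There is a sample on the last dosing day, and later ones at SFU and, in Sequence A, on Day 33 or 25. They can show a persisting change but come too late to spare PSL.
- **The liver rule has no function.** Also wrong. The Day 17 sample could prevent PSL from starting in Sequence B, and in Sequence A the Day 19/33 or Day 11/25 results could stop the later OC-only dose.
- **The last-day sample says nothing about the top dose.** Not in Part 2, where a pre-dose sample would follow nine days at 200mg BID.
- **The SAP presents the Part 1 sample as an on-dose 400mg BID value.** No text says so. SAP Section 10.3 summarises by time point and sequence, so no relabelling is needed.
- **Participants were harmed or exposed to a known liver risk.** Nothing in the documents supports this.

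**Conclusion.** The point holds as a low-cost improvement. The first scheduled chemistry result during PSL dosing comes after 98% of the planned PSL in Part 1 (11,400 of 11,600 mg) and 95% in Part 2 (3,800 of 4,000 mg). The 200 mg is an upper bound. If the taper requirement in Section 7.1 applies despite the immediate stop in Section 7.1.1, the last-day sample spares effectively nothing, because that day is itself part of the taper.

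The dose counts follow directly from the protocol tables. The conclusion also rests on Day 36 as shown in SAP Table 2-5 and on the Table 10-2 threshold. It concerns scheduled results and PSL only. Whether an individual participant had an unscheduled test cannot be determined from these documents.

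**What to change.** In the Schedules of Activities, add a chemistry/hematology tube to the pre-dose PK draw on the day before OC dosing: Day 8 or 25 in Tables 1-6 and 1-7, and Day 12 or 29 in Tables 1-4 and 1-5 if that schedule is reused. Require the result to be reviewed before the next dosing day. This day follows six full days at top dose in both parts and allows review before the OC dose. The Part 1 Day 8 or 25 trough draw is an alternative: it leaves more PSL stoppable but follows only two days at 400mg BID.

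The cost is one small tube and its assay, with no added visit or venepuncture. Neither tube volume nor planned total is given, so the total must be re-added against the 500mL limit in Section 8; an assumed 5 to 10 mL would be 5/500 = 1% to 10/500 = 2% of it. A participant stopped before the OC dose would also lose her PSL+OC primary-endpoint data, although Section 1.1.6 allows replacement. Part 1 reporting needs no change.
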